If there are no alternative procedures or treatments, select "No". Examples of advantageous alternatives: earning extra class credit in some time-equivalent way other than research participation; obtaining supportive care or a standard clinical treatment from a health care provider instead of participating in research with an experimental drug.

	No
	Yes

→ If yes, describe the alternatives.

5.13 Upload to the Supporting Documents SmartForm of **Zipline** all data collection forms (if any) that will be directly used by or with the subjects, and any scripts/talking points you will use to collect the data. Do not include data collection forms that will be used to abstract data from other sources (such as medical or academic records, or video recordings).

- *Examples: survey, questionnaires, subject logs or diaries, focus group questions.*
- *NOTE: Sometimes the IRB can approve the general content of surveys and other data collection instruments rather than the specific form itself. This prevents the need to submit a modification request for future minor changes that do not add new topics or increase the sensitivity of the questions. To request this general approval, use the text box below to identify the questionnaires/surveys/ etc. for which you are seeking this more general approval. Then briefly describe the scope of the topics you will cover and the most personal and sensitive questions. The HSD staff person who screens this application will let you know whether this is sufficient or whether you will need to provide more information.*
- *For materials that cannot be uploaded: upload screenshots or written descriptions that are sufficient to enable the IRB to understand the types of data that will be collected and the nature of the experience for the participant. You may also provide URLs (website addresses) or written descriptions below. Examples of materials that usually cannot be uploaded: mobile apps; computer-administered test; licensed and restricted standardized tests.*
- *For data that will be gathered in an evolving way: This refers to data collection/questions that are not pre-determined but rather are shaped during interactions with participants in response to observations and responses made during those interactions. If this applies to your research, provide a description of the process by which you will establish the data collection/questions as you interact with subjects, how you will document your data collection/questions, the topics you plan to address, the most sensitive type of information you will plan to gather, and the limitations (if any) on topics you will raise or pursue.*

Use this text box (if desired) to provide:

Short written descriptions of materials that cannot be uploaded, such as URLs

A description of the process you will use for data that will be gathered in an evolving way.

- The general content of questionnaires, surveys and similar instruments for which you are seeking general approval. (See the **NOTE** bullet point in the instructions above.)

Primary data collection method will be via semi-structure interviews (Aims 1 & 2), and REDCap surveys – PDF versions of these surveys will be attached (Aim 3).

5.14 Send HSD a Confidentiality Agreement if you will obtain or use any private identifiable UW records without subject's written consent (for example, screening medical records or class grades to identify possible subjects).

The Confidentiality Agreement form must be completed, printed, signed, and mailed to the Human Subjects Division at [name]. Your IRB application cannot be approved until we receive the Confidentiality Agreement.

6 CHILDREN (MINORS) and PARENTAL PERMISSION

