A blocked randomization scheme will be generated using an online program will be used to derive randomization assignment, programmed in the internet sleep intervention, and not accessible to study investigators. Enrolled participants will be continuously randomized

T1 BASELINE ASSESSMENT

A member of the research team will connect with eligible and interested participant children and their parent at convenient time, will talk about the purpose of the study, and obtain consent from parent/caregiver participants (see SLEEPSMART Consent in Appendix A). Child assent will then be obtained and copies of both documents given to the parent (see SLEEPSMART Assent in Appendix A).

After consent and assent, JIA children and their parent will be given a link with the electronic instruments preloaded and instructed to complete the instruments to the best of their ability. If questions arise, a member of the research team will answer as needed. This technique was successfully used in [name] and [name]'s prior intervention studies. The surveys for T1, T2, and T3 will take 30 to 35 minutes to complete.

**Table 1. Summary of T Assessments – All T1, T2, and T3 unless otherwise indicated
(T1 [Baseline], T2 [immediately post intervention], T3 [1 month post intervention])**

Parent Items	Estimated Time (minutes)/Assessment	Child Items	Estimated Time (minutes)
Demographics (age, gender, race, ethnicity, income; child age, race, ethnicity; medications) Childhood assessment questionnaire	5 T1 T1		
Self-management measures Self-efficacy to Manage Chronic Disease Scale Decision Balance sheet Goal setting (# and types of goals created of goals tracked and rate of goals) Credibility/Expectancy Questionnaire	<5	Self-management measures Child Self-efficacy Scale Patient activation measure Index of self-regulation Goal setting (# and types of goals created of goals tracked and rate of goals) Sleep problems questionnaire	<5
SYMPTOMS PROMIS 29 profile PROMIS Sleep disturbance -adult PROMIS sleep-related impairment	<5	SYMPTOMS PROMIS Peds Profile (physical function, anxiety, depression, fatigue, peer relationships, pain interference). PROMIS Sleep disturbance PedsQL Multidimensional Fatigue	10

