Children's Sleep Hygiene Scale Children's Sleep Wake scale Children's Sleep Habits Questionnaire Dysfunctional Beliefs about sleep scale Pittsburgh sleep quality index	15 T1	Adolescent Sleep Hygiene Scale Adolescents Sleep Wake scale Dysfunctional Beliefs about sleep scale Pre-Sleep Arousal Scale Morning Eveningness questionnaire	15 T1 T1
Health Outcomes PROMIS Global Health PedsQL Family Impact Module Health Care Utilization	5	Health Outcomes Health-related Quality of Life Questionnaire PROMIS Global health	5
Treatment Evaluation Inventory (Acceptability) Sleepsmart end of Survey	<5 T3 T3	Treatment Evaluation Inventory (Acceptability) Sleepsmart end of Survey	<5 T3 T3

Actigraphy After completing the above instruments at baseline, a member of the research team will give the parent and child the actigraph. The actigraph will be worn by children and parents (on non-dominant wrist) continuously for 10 days. Both will be instructed in the application of the monitors including removal during bathing, swimming, and how to assess for appropriate fit using the monitor band. Both will be instructed to document times when the actigraphy monitor is removed and replaced using the diary. Actigraphs will be

collected at the end of the 10 days of recording using a prepaid padded envelope. Sleep variables obtained via actigraphy include sleep onset, sleep offset, sleep period time, mean activity during sleep, mean number of minutes of sleep and wake, percentage of sleep and wake within the sleep period, and number of waking episodes during the sleep period. These variables are used to derive total sleep time, percent sleep efficiency (SE, sleep time/time in bed x 100), percent wake after sleep onset (WASO, wake min/sleep time x 100), and a fragmentation index (of waking episodes/hr). These variables will enable us to reliably characterize sleep quality as it is occurring in the home environment.

Electronic Sleep Diary (wake time and bedtime)

Parents and children will record their daily sleep. A standard log of sleep activities (time to bed, sleep onset, awakenings, quality) will be completed daily in the morning upon awakening and prior to bedtime using a previously established and tested sleep diary.

SLEEPSMART INTERVENTION (ONLY Treatment group receives this)

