Actigraphy	Actiwatch 64 Small wrist watch that measures body movement and estimates of total sleep time, amount of wake, sleep quality, bedtime and waketime variability.
Sleep diary	Electronic daily sleep and pain diary-children and parents will complete an electronic sleep diary twice a day for 10 days. Children and parents will complete the diary at bedtime and upon waking (what time you went to bed, wake up, # and duration of night awakenings), events that may disrupt your sleep (anxious about a test; hobbies [music recital, basketball game, school event], parent out of town, fight with a friend, homework, sickness).

Below questionnaires to be completed by treatment group only:

Treatment Evaluation Inventory and End of Study Survey **Acceptability Survey** only the treatment group will complete this survey. 11-item survey to be used in post-intervention interview with parent and child. Survey includes 6 open-ended questions and 5 Likert scale questions (1=strongly disagree, 5=strongly agree). Items assess participant acceptability of various components of the SLEEPSMART Study.

5.3 Data sources. For all types of data that you will access or collect for this research: Identify whether you are obtaining the data from the subjects (or subjects' specimens) or whether you are obtaining the data from some other source (and identify the source).

If you have already provided this information in Question 5.1, you do not need to repeat the information here.

Data will be obtained from the child and parents in the form of:

Aims 1 & 2: semi-structured interviews, & videotaping, and testing of the REDCap SLEEPSMART Website use – site tracks unique ID logon date, time, duration;

Aim 3: surveys (REDCap), sleep diaries (REDCap), and wrist watch. REDCap SLEEPSMART Website use – site tracks unique ID logon date, time, duration.

The CRA at SCH will collect information from the child's medical record (name, age, sex, phone number, address), JIA form (disease duration, onset of symptoms, JIA type, active or inactive disease). The research staff at CHOP will not collect this information, rather parents will complete demographic survey that includes child age, gender, disease duration, JIA type, and active or inactive disease.

5.4 Retrospective/prospective.

For all types of data and specimens that you will access or collect for this research:

Describe which data are:

- Retrospective (i.e., exist at the time when you submit this application)

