Aim 2. Determine feasibility and initial efficacy of the SMID with children with JIA in a pilot RCT. We will determine study accrual and dropout rates as well as levels of patient acceptability and engagement in a pilot randomized controlled trial (RCT) comparing usual care to SMID intervention. Preliminary effect sizes of the SMID will be determined in youth receiving treatment compared to usual care on primary outcomes of actigraphy sleep duration, sleep quality, and feasibility/acceptability, and secondary outcomes of child and parent self-management (activation, motivation, self-efficacy), technology use, recommendations for innovative sleep monitoring. We hypothesize that children who receive technology-based SMID vs. those who receive Usual Care will achieve increased sleep duration and efficiency (quality), immediately post-treatment and at 3 month follow-up.

Sample. Sixty children, 9-11 years, diagnosed with JIA and one parent will be recruited from the Pediatric Rheumatology Clinic at SCH and remotely via a flyer on the JIA foundation website.

Recruitment. At SCH, the clinical research assistant (CRA) will give eligible JIA families a study information flyer; the flyer will also be posted on the WA JIA website. For both SCH and the JIA website, interested families will contact the CRA by calling a phone number on the study flyer. The CRA will describe the study and screen for participation. Interested participants will be sent a consent/assent forms by mail, with a prepaid envelope. The recruitment methods were fruitful in our prior studies. Inclusion and exclusion criteria for JIA children and parents is above. Gender/minority inclusion: Girls and boys are eligible; we expect to enroll more Caucasian girls because the heightened disease prevalence among Caucasian girls and its relatively low prevalence in other ethnic groups.^{57,58} JIA patients seen at SCH approximate the national ratio of female:male patients 4:1 and 95% Caucasian. Biologic variables: We will include sex as covariate in the statistical analysis due to the potential confounding effect on sleep.

Measures. **Table 2** shows the measurement plan for the study assessments.^{2-27,59-72}

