homework and practice to change behavior, several components (e.g., positive feedback loops) actively encourage user attention and motivation in order to promote skills acquisition and rehearsal. The intervention will be interactive and personalized with tailored feedback. Using a diary function on the web site, children track their sleep in real-time and can generate customized reports and graphs from their data. Modules will take an estimated 20 minutes to complete and will include multimedia elements to enhance learning. Participants will be asked to spend additional time practicing skills and completing assignments at the end of each module. A message center will allow each child and/or parent to ask questions as they progress in the program. The PI will review messages, provide individualized feedback through Web message center. The web site uses a multimedia-rich format (e.g., animations, videos, audio clips) to deliver content. The website is built on a responsive platform and can be viewed on multiple devices (e.g., smartphones, laptops, tablets) to increase ease and flexibility of use. All app and website content is (a) written at a grade 4th grade reading level, (b) developmentally appropriate for 9-11 year-olds, and (c) is based on a unifying theme/narrative.

Measurement Plan. Assessment will occur at (T1 baseline), immediately after intervention (T2) and repeated at 3 months post-intervention (T3) for both the SMID and usual care groups. All questionnaires will be administered using REDCap, a secure web-based tracking and on-line data acquisition system. Children will wear an actigraph a reliable and validated measure of sleep²⁵⁻²⁷ on their non-dominant wrist for 10 consecutive days, and complete an electronic symptom diary. After 10 days, parents will mail back the actiwatches in a prepaid self-addressed envelope used in PIs prior sleep studies.^{1,27,35} Actigraphy data will be downloaded, scored, and a member of the team will follow up with parents to discuss the baseline sleep patterns within 1 week. Estimated time burden is 20 minutes for children and 10 minutes for parents. Response burden is minimized by online administration, which saves and stores responses.

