Data will be reviewed for completeness and errors including consistency checks for relevant variables. Tabular and graphical methods of data exploration including frequency tables and scatterplots will be used to explore distributions of study variables. We will adjust for sex, and considered use of either RM ANCOVA or generalized estimating equations (GEE) to evaluate intervention effects. We prefer GEE since it allows us to account for clustering of repeated assessments within individuals as well as the longitudinal nature of the data and provides higher power. Missing data will be examined for patterns and we will employ GEE multiple imputation to carry out ITT analysis. Single degree of freedom contrasts by group will be examined if there are significant changes in sleep measures from pre- to post-treatment and/or from pre- to 3-month follow-up for SMID vs Usual Care. Secondary treatment outcomes will be examined using GEE to explore for mean changes across time and between groups using interaction terms and contrasts. The range of outcome measures will allow us to obtain experience with alternative measures of sleep, self-management measures that will inform our future research. Outcome data will also be used to generate effect size point estimates for the future large-scale trial. **Design Considerations, Alternative Strategies and Timeline.** Project constraints on research time and resources will pose study limitations, which we have adjusted for in the study design and timeline. As the study requires participant enrollment for 5 months, we anticipate some challenges around retention, and have addressed this with a number of strategies described below. Co-I, [name] successfully recruited and retained youth with chronic pain in Web-based interventions over a period of 12 months (>90% retention). An attention control group and other parent/child variables were considered but feasibility, acceptability, and proof of concept were prioritized for this initial phase. **Rigor and Transparency** will be ensured by: 1) the proposed methods (usability, expert panel, parent/child input); 2) use of successful retention strategies from prior studies; 3) documentation of attrition; 4) sample size derived from a priori power analysis; 5) statistical methods to account missing data and change overtime. **Retention.** We will make every effort to retain participants with fruitful methods used in our prior studies including: 1) automated reminders built into the Web program; 2) phone calls scheduled at convenient times, 3) incentives for completion of each assessment (\$20 gift card/each Aim 1; Aim 2 [T1 \$40 gift card each; T2 \$60 gift card each; T3 \$80 gift card each]), 3) semi-structured interviews *prior to* intervention development; and 4) exit interviews post-intervention. **Strengths** include: 1) successful recruitment of JIA children; 2) expertise in sleep, technology-based interventions, usability assessments; 3) leveraging of successful methods in a prior Web-based interface; 4) development of the first low resource demand, convenient, and personalized sleep self-management intervention for JIA. Findings generated will address important methodological issues needed to develop innovative sleep self-management intervention for children with chronic illnesses and their parents.

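### The 10-day sleep recordings are neither scheduled around nor adjusted for school nights, which leaves a cheap but minor precision gain unused

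*Combined protocol and SAP*

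**What the plan says.** The Research Strategy (Aim 2) lists "primary outcomes of actigraphy sleep duration, sleep quality, and feasibility/acceptability". The recording window is ten days at each visit: "The actigraph will be worn by children and parents (on non-dominant wrist) continuously for 10 days" in section 5.1, and "on their non-dominant wrist for 10 consecutive days" in the Measurement Plan. Neither place fixes a start day, a mix of school and school-free nights, or a term for the window. Among the actigraphy variables, section 5.1 lists "mean number of minutes of sleep and wake", with no split by type of night.

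The diary in section 5.1 is described so: "A standard log of sleep activities (time to bed, sleep onset, awakenings, quality) will be completed daily in the morning". Section 5.2 adds "events that may disrupt your sleep (anxious about a test", followed by homework, school events and other examples. The measures table in the Research Strategy also lists daytime activities at T1, T2 and T3. None of these listed items states whether the next day is a school day.

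On timing, section 5.1 says "Enrolled participants will be continuously randomized". The Data Analysis Plan says "We will adjust for sex, and considered use of either RM ANCOVA or generalized estimating equations (GEE) to evaluate intervention effects", with GEE preferred. No other covariate is named.

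**The concern.** The plan itself treats homework, tests and school events as things that disturb sleep, so it accepts that school affects the outcome. A child recorded in term at T1 and in a school break at T2 may show a change in sleep duration that has nothing to do with the intervention. Sex cannot absorb this: it is constant within a child, so as a main effect it drops out of a T1-to-T2 change.

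At stake is precision. Calendar variation widens the SD of change in a primary outcome of a small pilot, one of whose stated purposes is to supply effect sizes for a definitive trial. The information needed to remove it is simple to collect when the diary is filled in. It is harder to rebuild later, because families come from Seattle, Philadelphia and social media, and school calendars differ.

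**Working it through.** **Inputs from the documents**
- 60 dyads enrolled, 50 analysed (25 per group), three measures, correlation 0.3, d = 0.48 for total sleep time, stated power 80-90% (Research Strategy, Power).
- T1-to-T2 gap, start to start. Lower end: 8 weeks = 56 days, the T2 time in section 5.1. Upper end: 10 days of wear + 21 days (the longer of 2-3 weeks) + 56 days (the 8-week intervention in the Research Strategy) = 87 days, about 12 weeks.

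**Assumed, because the documents give no figure**
- SD of a visit mean: 45-60 min.
- Extra sleep on a school-free night: 20, 40 or 60 min.
- Break weeks per year: 10 to 13.
- Starts spread evenly over the year.
- Two-sided alpha of 0.05.

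**Step 1: the plan's power.** For the group-by-time interaction, λ = (d/2)² × N × m / (1 − ρ) = 0.24² × 50 × 3 / 0.7 = 12.34 on 2 and 96 df. This gives 88.2%, inside the stated 80-90%. The stated power is reproduced.

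**Step 2: how much the night mix changes.** Friday and Saturday nights count as free, as does every night in a break. Sliding two 10-night windows, 56 to 87 days apart, along such calendars gives an SD for the T2-minus-T1 change in the share of free nights of about 0.39-0.48. Between a third and a little under half of children change by 0.4 or more. The mean change is zero under even enrolment.

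**Step 3: share of change-score variance.** Change variance = 2 × SD² × (1 − 0.3) = 1.4 × SD², which is 2,835 min² at SD 45 and 5,040 min² at SD 60. Calendar part = (shift × SD of share)².

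| Extra sleep on a free night | Low: share SD 0.39, SD 60 | High: share SD 0.48, SD 45 |
|---|---|---|
| 20 min | 7.8² / 5,040 = 1.2% | 9.6² / 2,835 = 3.3% |
| 40 min | 15.6² / 5,040 = 4.8% | 19.2² / 2,835 = 13.0% |
| 60 min | 23.4² / 5,040 = 10.9% | 28.8² / 2,835 = 29.3% |

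If adjustment removed all of it, the standard error would shrink by the factor √(1 − share): by under 1% at a share of 1.2%, 7% at 13.0%, and 16% at 29.3%.

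**Step 4: a second calendar, with the noise added on top of the plan's variance.** With about 14 break weeks, a 77-day gap, variance of the share change 0.234 and SD 50 (change variance 3,500), shifts of 15, 30, 45 and 60 min inflate the variance by 1.5%, 6%, 14% and 24%. Dividing λ by that inflation takes power from 88.2% to 87.7%, 86.2%, 83.6% and 80.0%. Over SD 40-60 min, the lowest value is 75.5% (SD 40, shift 60).

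**Step 5: chance difference between arms.** At a 40-min shift with unblocked assignment, SD = 40 × (0.39 to 0.48) × √(2/25) = 4.4 to 5.4 min. The documents specify blocks but no size. Simulating blocks of 4 or 6 with enrolment over 6-18 months gives about 2-4 min. The standard error of the change contrast is √(1.4 × SD² × 2/25) = 15 min at SD 45 and 20 min at SD 60.

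**The case against.** The strongest case against the point is that the data are probably recoverable and the effect may be small. Diary entries are made daily, so weekday or weekend should follow from dates. School events and daytime activities are listed. The diary form is not in the text, because the Aim 3 survey forms are attached separately. A reader might infer that school nights go unrecorded, but the documents do not establish that. They show only that no such item is listed and that no use of one is planned. This part of the objection stands.

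A reader might also infer that enrolment is year-round. The documents never say so. They give 3 months for Aim 3 in section 5.1, with unclear scope, and 5 months of participation in the Research Strategy. If starts were concentrated in one part of the year, the noise would fall: with a 77-day gap, the variance of the share change is 0.103 for starts from September to February and 0.090 for March to May, against 0.234 for the full year.

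Two stronger readings fail:
- **Full switch set against the effect sought.** A child who moves from term to vacation shifts by 40 × (1 − 2/7) = 29 min at a 40-min effect, which looks like the 22-29 min that d = 0.48 implies at SD 45-60. But the first figure is one child's shift and the second a difference between arm means. Switches occur in both arms, and their common part falls into the visit effect.
- **Chance imbalance distorts the estimate.** Blocked, continuous randomization puts children who start close together into both arms. A chance difference of 2-4 min is small against a standard error of 15-20 min.

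Finally, a definitive trial run the same way would carry the same calendar variance, and d = 0.48 may already include it. So an unadjusted SD is not wrong for planning such a trial. That also stands, and it is why both SDs should be reported.

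**Conclusion.** The point holds as a minor, inexpensive improvement in precision. As written, the plan neither schedules around school nights nor adjusts for them, and the T1-to-T2 gap makes moves between term and break plausible for some children. The consequence is extra variance in the sleep-duration change, with no expected bias as long as both arms follow the same visit schedule.

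Its size cannot be fixed from the documents. It is about 1-3% of change-score variance at a 20-min school-night effect, 5-13% at 40 min and 11-29% at 60 min, under the assumed enrolment pattern, break weeks and SDs and the plan's correlation of 0.3. The calculation covers sleep duration only, not efficiency. The stated power is not in error: even with calendar noise added on top, it leaves the 80-90% range only when a large shift meets a small SD.

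**What to change.** - **Record it.** Add one yes/no item on whether there is school tomorrow to the existing bedtime diary, at T1, T2 and T3 in both arms. If the attached form already has such an item, say so. Otherwise state that status will be derived from dated nights and each child's school calendar.
- **Use it.** Pre-specify a school-night term in the preferred GEE, fitted to nightly sleep duration and efficiency and clustered by child. The alternative is to adjust each visit mean for its share of school-free nights. The intervention does not alter the school calendar, so the adjustment does not remove any treatment effect.
- **Report both.** Give adjusted and unadjusted SDs of change, so that the definitive trial can be planned under either analysis.

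The cost is slightly more diary burden and one model degree of freedom.
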